03 DEC 2019

[name], M.Sc., FAAP, FRCPC
Head, Clinical Research and Development
American Regent, Inc.

Date

03-December-2019

[name]
Medical Director, Clinical Research and Development
American Regent, Inc.

Date

Study Synopsis

Protocol No. 1VIT18045

Title:	Evaluating the Efficacy and Safety of Intravenous Ferric Carboxymaltose in Pediatric Patients with Iron Deficiency Anemia and an Unsatisfactory Response to Oral Iron under Study Protocol 1VIT17044
Study Drug:	Injectafer® (Ferric Carboxymaltose [FCM])
Objectives:	
 The primary objective of this study is to evaluate the efficacy and safety of intravenous (IV) ferric carboxymaltose (FCM) in pediatric participants who have iron deficiency anemia (IDA).
Nature of Study:	Phase III
Design:	
This is a single arm, open-label, multi-center, multi-national, non-randomized study that will evaluate the efficacy and safety of a one course treatment with FCM in participants who had an unsatisfactory response to oral iron in study 1VIT17044.
 
Subjects will have an End of Study (EOS) Visit (Day 35) from the 1VIT17044 study to qualify for entry. Subjects will then be screened, meet all inclusion criteria, no exclusion criteria and have a baseline evaluation. Based on the successful completion of the baseline evaluations, subjects will be enrolled and will receive the first dose of FCM (Day 0). The second FCM dose will occur 7 days from the first dose. Subjects will return to the clinic 14 and 28 days post their first dose for laboratory and safety assessments, and at 35 days post the first dose, participants will return to the clinic for final safety and efficacy assessments. Once all assessments are complete the participant will exit the study.
 
An unsatisfactory response to oral iron (i.e., an increase in hemoglobin (Hgb) of <1 g/dL from baseline) will be defined as non-responders to oral iron treatment. Non-responders who continue to meet all inclusion criteria (including Hgb <11 g/dL) and none of the exclusion criteria will receive 1 course of FCM.

Inclusion Criteria:	
 Unsatisfactory response to oral iron or those that required a concomitant intervention, (defined as, blood transfusion, use of IV or oral iron outside of protocol, increase in erythropoietin for any reason [Day 0 thru Day

CONFIDENTIAL

American Regent, Inc.

Protocol No.: 1VIT18045

Administrative Change 1 Date: Final 03 December 2019

	
35 of study protocol 1VIT17044], change in Inflammatory Bowel Disease [IBD] treatment).
 
2. Hgb <11 g/dL3. Ferritin ≤300 ng/mL and Transferrin Saturation (TSAT) <30%
Exclusion Criteria:	
1. Known history of hypersensitivity reaction to any component of FCM.2. History of acquired iron overload, hemochromatosis, or other iron accumulation disorders.3. History of significant diseases of the liver, hematopoietic system, cardiovascular system, psychiatric disorder, or other conditions which, in the opinion of the investigator, may place a subject at added risk for participation in the study.4. Any existing non-viral infection.5. Known history of positive hepatitis B surface antigen (HBsAg) or hepatitis C viral antibody (HCV) with evidence of active hepatitis.6. Known history of positive human immunodeficiency virus (HIV-1/HIV-2) antibodies (anti-HIV).7. Anemia due to reasons other than iron deficiency (e.g., hemoglobinopathy and vitamin B12 or folic acid deficiency) that has not been corrected.8. Administration and / or use of an investigational product (drug or device) within 30 days of screening.9. Alcohol or drug abuse within the past six months.10. Female participant who is pregnant or lactating, or sexually active females who are of childbearing potential not willing to use an acceptable form of contraceptive precautions during the study.11. Unable to comply with study procedures and assessments.
Study Drug Administration	Participants will receive 2 doses (Day 0 and Day 7) of FCM at 15 mg/kg to a maximum single dose of 750 mg (whichever is smaller) up to a maximum total dose of 1500 mg. FCM will be administered as either an undiluted IV push at a rate of 100 mg (2 mL)/minute OR in no more than 250 mL of normal saline and infused over 15 minutes
Endpoints:	
Primary Endpoint:
 
• Change in Hgb from baseline to Day 35 
Secondary Endpoints:
 
• Change in ferritin from baseline to Day 35• Change in TSAT from baseline to Day 35

[figure not shown]
CONFIDENTIAL

American Regent, Inc.

Protocol No.: 1VIT18045

Administrative Change 1 Date: Final 03 December 2019

	
• Changes from baseline in Hgb, ferritin, TSAT, and reticulocyte hemoglobin content (CHr) throughout the study
Participant Duration:	35 Days
Study Sites:	Approximately 25 sites

9.2. Investigator Responsibilities	31
9.3. Financial Disclosure	31
9.4. Advertisement for Participant Recruitment	32
9.5. Documents Required for Study Initiation	32
9.6. Quality Control and Quality Assurance	32
9.6.1. Investigator Selection Criteria	32
9.6.2. Clinical Monitoring	33
9.6.3. Quality Assurance Audit	33
9.7. Ethics	33
9.7.1. Ethical and Legal Issues	33
9.7.2. Institutional Review Board	33
9.7.3. Informed Consent	34
9.7.4. Good Clinical Practice	34
9.8. Data Handling and Record Keeping	34
9.8.1. Case Report Form	34
9.8.2. Confidentiality	35
9.8.3. Termination of the Study	35
9.8.4. Protocol Revisions	35
9.8.5. Protocol Administrative Changes	36
9.9. Publication Policy	36
10. INVESTIGATOR'S ACKNOWLEDGEMENT	37
11. REFERENCES	38
12. APPENDIX 1: AMENDMENT/ADMINISTRATIVE CHANGES	39
12.1. ADMINISTRATIVE CHANGE 1	39

CONFIDENTIAL

American Regent, Inc.

Protocol No.: 1VIT18045

Administrative Change 1 Date: Final 03 December 2019

CONFIDENTIAL

American Regent, Inc.

Protocol No.: 1VIT18045

Administrative Change 1 Date: Final 03 December 2019

LIST OF TABLES

		PAGE
Table 1	Schedule of Activities	17
Table 2	Grading of Adverse Event Severity	25

LIST OF FIGURES

		PAGE
Figure 1	Study diagram.....	6

LIST OF ABBREVIATIONS

AE	Adverse Event
ALT	Alanine Aminotransferase
Anti-HIV	Antibodies to Human Immunodeficiency Virus
AST	Aspartate Aminotransferase
BUN	Blood Urea Nitrogen
CFR	Code of Federal Regulations
CHr	Reticulocyte Hemoglobin Content
CTCAE	Common Terminology Criteria for Adverse Events
dl	Deciliter
eCRF	Electronic Case Report Form
e.g.	For Example
EOS.	End of Study
FCM	Ferric Carboxymaltose
FDA	Food and Drug Administration
Fe	Iron
g	Gram
GCP	Good Clinical Practice
GGT	Gamma-Glutamyl Transferase
GMP	Good Manufacturing Practice
Hct	Hematocrit
HBsAg	Hepatitis B Surface Antigen
HCV	Hepatitis C Viral Antibody
Hgb	Hemoglobin
HIV	Human Immunodeficiency Virus
IBD	Inflammatory Bowel Disease
ICH	International Conference on Harmonisation
IDA	Iron Deficiency Anemia
i.e.	That Is
IND	Investigational New Drug Application
IRB	Institutional Review Board
IRT	Interactive Response Technology
IV	Intravenous
Kg	Kilogram
L	Liter
LDH	Lactic Dehydrogenase
MCH	Mean Corpuscular Hemoglobin
MCHC	Mean Corpuscular Hemoglobin Concentration
MCV	Mean Corpuscular Volume
MedDRA	Medical Dictionary for Regulatory Activities
m	Meter
mg	Milligram
mL	Milliliter

CONFIDENTIAL

American Regent, Inc.

Protocol No.: 1VIT18045

Administrative Change 1 Date: Final 03 December 2019

NCI	National Cancer Institute
ng	Nanogram
PCS	Potentially Clinically Significant
PT	Preferred Term
RBC	Red Blood Cell
RDW	Red (cell) Distribution Width
SAE	Serious Adverse Event
SAP	Statistical Analysis Plan
SD	Standard Deviation
SOC	System Organ Class
TEAE	Treatment Emergent Adverse Event
TIBC	Total Iron Binding Capacity
TSAT	Transferrin Saturation
US	United States
WBC	White Blood Cell

1. INTRODUCTION

1.1. Treatment of Iron Deficiency Anemia

Iron deficiency anemia (IDA) remains the most common nutritional deficiency in children in the United States (US) [Looker, 1997]. Rapid growth, insufficient dietary intake, and limited absorption of dietary iron combine to place children at increased risk for iron deficiency. Iron malabsorption, gastrointestinal blood loss, or iatrogenesis due to repeated blood sampling all represent common clinical mechanisms that can result in IDA. Even when recognized, some children are unable to tolerate prescribed oral iron supplementation or are unresponsive to it [Kulnigg, 2006]. Anemia may also decrease survival rates in adults and children with chronic renal impairment where it is a commonly encountered problem [Foley, 1996; Staples, 2010]. In addition, under-recognized or inadequately treated anemia is likely the most common extra-intestinal manifestation of IBD in children, and it can result in a decrease in quality of life and increased morbidity, inclusive of hospitalization, in affected patients [Kulnigg, 2006].

Non-hematologic consequences of iron deficiency in children include poor weight gain, anorexia, irritability, decreased attention span, exercise intolerance, and decreased physical activity [Wharton, 1999]. Existing data suggests that chronic IDA in infants and toddlers is associated with long-term diminished mental, motor, and behavioral functioning. Although the exact relationship between iron deficiency and its detrimental effects on growth and development is not well-understood, it appears that these effects do not occur until iron deficiency becomes severe and chronic enough to produce anemia [Kazal, 2002].

Options for correcting iron deficiency include both oral and parenteral formulations. As previously described, some children are unable to tolerate or are non-responsive to oral iron. Blood transfusion is an option to treat anemia and replete iron stores, but often scarce supply, as well as the potential risk of blood-borne pathogens, limits its use to severely ill or clinically unstable patients [Kulnigg, 2006]. In view of the limitations associated with oral iron administration or blood transfusions, IV iron administration is an important therapeutic option for use in patients with IDA [Powers, 2014].

Multiple parenteral iron products are available. These products vary in the way that iron is complexed, which influences the total amount of iron that may be administered during a single administration. Numerous other differences differentiate the products. However, all appear to effectively release iron post administration and can restore iron deficit in the patient. Previous studies with parenteral iron sucrose (Venofer®) have been performed in the pediatric population [Michaud, 2002; Pinsky, 2008; Surico, 2002]. Iron doses have varied in these studies, and the data demonstrates the efficacy and safety of Venofer® in doses up to 7 mg iron/kg (or 200 mg) administered over 3 minutes, which was shown to be beneficial to both the child and health care facility [Michaud, 2002].

Ferric Carboxymaltose has been characterized as an iron complex (Type 1) with a molecular mass of about 150,000 Daltons. The solution is a dark brown color with a near

neutral pH (5.0 to 7.0) and a physiological osmolarity permitting administration of higher single doses in short time periods. Although no randomized interventional studies have been completed with FCM in the pediatric population to date, the product has been used successfully to address iron deficiency in pediatric patients with ulcerative colitis and Crohn's disease. A non-interventional, retrospective observational data collection reported FCM exposure in 79 patients aged 2 to 18 years with a mean age of 12.7 years. In these patients, FCM was found to be safe, well-tolerated, and effective in increasing Hgb, ferritin, and TSAT [Favreau, 2017].

The proposed study will provide safety and efficacy data on the use of FCM in pediatric patients (aged between 1 and 18 years) with IDA. FCM will be administered in 2 doses at 15 mg/kg maximum single dose of 750 mg with a total maximum cumulative dose of 1500 mg. The ability to infuse higher doses of elemental iron should permit repletion in fewer overall infusions, and in doing so may ultimately permit fewer visits to the treating facilities.

1.2. Ferric Carboxymaltose

1.2.1. Key features of Ferric Carboxymaltose

Ferric Carboxymaltose injection is a stable, non-dextran, Type I polynuclear iron (III)-hydroxide carbohydrate complex developed as an IV iron replacement therapy for the treatment of IDA. After IV administration, FCM is mainly found in the liver, spleen, and bone marrow. The iron slowly dissociates from the complex and can be efficiently used in the bone marrow for Hgb synthesis. The carbohydrate moiety of FCM is metabolized by the glycolytic pathway.

1.2.2. Ferric Carboxymaltose versus Other Parenteral Iron Agents

There is considerable efficacy and safety data in the literature with respect to existing parenteral iron formulations [Staples, 2010]. However, prior to the approval of non-dextran formulations, the risk of systemic adverse reactions restricted their use. FCM offers significant advantages compared to other available IV iron preparations.

Iron dextran, the first parenteral iron product available in the US, has been associated with an incidence of anaphylaxis/anaphylactoid reactions (i.e., dyspnea, wheezing, hypotension, urticaria, angioedema) as high as 1.7% [Michaud, 2002]. Over the last 20 years, 30 deaths have been attributed to the use of IV iron dextran [Fishbane, 2003]. The high incidence of anaphylaxis/anaphylactoid reactions is believed to be caused by the formation of antibodies to the dextran moiety. Although some have suggested that high molecular weight iron dextran is associated with a higher rate of life threatening adverse events and anaphylactic reactions in comparison to low molecular weight iron dextran, the US Food and Drug Administration (FDA) was unable to find a clear difference after an examination of post-marketing data, clinical trial data, death certificates, and emergency room diagnoses [Pinsky, 2008]. Iron dextran is limited to second line therapy for treatment of iron deficiency.

More recently approved IV iron formulations, including iron sucrose and iron gluconate, do not contain the dextran moiety. However, they too have significant dosage and administration rate limitations. If the body's ability to sequester, store, and transport infused iron is overwhelmed, a reaction to excess free iron in circulation, referred to as a bioactive iron reaction, may occur. Iron sucrose and iron gluconate preparations carry a significant risk of inducing a bioactive iron reaction when delivered at higher doses. These reactions are characterized by hypotension (without allergic signs) accompanied by pain in the chest, abdomen, flank and/or nausea, vomiting, and diarrhea [Van Wyck, 2004].

Due to its structure, FCM is more stable than iron gluconate and iron sucrose, and this results in a slower delivery of the complexed iron to endogenous iron binding sites. These characteristics of FCM make it possible to administer much higher single doses over shorter periods of time than iron gluconate or iron sucrose, resulting in the need for fewer administrations to replete iron stores.

2. TRIAL OBJECTIVE

2.1. Primary Objective

The primary objective of this study is to evaluate the efficacy and safety of IV FCM in pediatric participants who have IDA.

3. OVERALL STUDY DESIGN AND RATIONALE

3.1. Overall Study Design

This is a single arm, open-label, multi-center, multi-national, non-randomized study that will evaluate the efficacy and safety of a one course treatment with FCM in participants who had an unsatisfactory response to oral iron in study 1VIT17044.

Subjects will have an EOS Visit (Day 35) from the 1VIT17044 study to qualify for entry. Subjects will then be screened, meet all inclusion criteria, no exclusion criteria and have a baseline evaluation. Based on the successful completion of the baseline evaluations, subjects will be enrolled and will receive the first dose of FCM (Day 0). The second FCM dose should occur 7 days from the first dose. Subjects will return to the clinic 14 and 28 days post their first dose for laboratory and safety assessments, and at 35 days post the first dose, participants will return to the clinic for final safety and efficacy assessments. Once all assessments are complete the participant will exit the study.

An **unsatisfactory response** to oral iron (i.e., an increase in Hgb of <1 g/dL from baseline) will be defined as non-responders to oral iron treatment. Non-responders who continue to meet all inclusion criteria (including Hgb <11 g/dL) and none of the exclusion criteria will receive 1 course of FCM.

3.2. Rationale of Study Design

The primary objective in this study is to allow participants who were randomized to receive oral iron in the 1VIT17044 trial and who had an unsatisfactory response to oral iron or those that required a concomitant intervention, (defined as, blood transfusion, use of IV or oral iron outside of protocol, increase in erythropoietin for any reason [Day 0 thru Day 35 of study protocol 1VIT17044], change in IBD treatment) to receive one course of FCM. This course of FCM will consist of two doses of FCM at 15 mg/kg (maximum single dose of 750 mg), separated by seven days.

This study is a rollover for study 1VIT17044 which is an open label, multi-center, multi-national, randomized, active-control parallel group study that will evaluate the efficacy and safety of FCM in pediatric participants, ages 1 to 18 years with iron deficiency anemia.

3.3. Schedule of Events

Table 1 Schedule of Activities

Procedures	Screening ¹ Day -7 to -1	Enrollment Visit 1, Day 0	Study Visit 2 Day 7 ± 1 day	Study Visit 3 Day 14 ± 1 day	Study Visit 4 Day 28 ± 1 day	Study Visit 5 Day 35 ± 1 day
Informed Consent / Assent	X					
Medical History	X					
Physical Exam		X				X
Inclusion/Exclusion Criteria	X	X				
Interactive Response Technology (IRT)	X	X				X
Vital Signs	X	X	X	X	X	X
Weight	X	X				
Height	X					
Temperature		X	X			
Blood sampling for Hematology, Chemistry and Iron Indices (5.5 mL) ¹	X	X	X	X	X	X
Blood sampling for Serum Pregnancy Test (1.5 mL), if applicable	X					X
Concomitant Medications	X	X	X	X	X	X
Adverse Event Assessments		X	X	X	X	X
FCM Dosing		X	X			

1. Note that there will be a 7 ± 1 day waiting period between 1VIT17044 end of study and extension screening

2. For a full description of central laboratory assessments, refer to Protocol Section 6.4.

4. PARTICIPANT SELECTION**4.1. Number and Type of Participants**

A maximum of approximately 36 participants from study 1VIT17044 who had an unsatisfactory response to oral iron.

4.2. Screening Phase

A subject who enters the screening phase will be assigned, via the IRT system, a unique screening number. Dietary iron intake will not be restricted during participation in the study.

If the participant does not qualify for study entry, the participant should be entered into the IRT system as a screen failure).

4.2.1. Inclusion Criteria

1. Unsatisfactory response to oral iron or those that required a concomitant intervention, (defined as, blood transfusion, use of IV or oral iron outside of protocol, increase in erythropoietin for any reason [Day 0 thru Day 35 of study protocol 1VIT17044], change in IBD treatment).
2. Hgb <11 g/dL
3. Ferritin \leq 300 ng/mL and TSAT <30%

4.2.2. Exclusion Criteria

1. Known history of hypersensitivity reaction to any component of FCM.
2. History of acquired iron overload, hemochromatosis, or other iron accumulation disorders.
3. History of significant diseases of the liver, hematopoietic system, cardiovascular system, psychiatric disorder, or other conditions which, in the opinion of the investigator, may place a subject at added risk for participation in the study.
4. Any existing non-viral infection.
5. Known history of positive HBsAg or HCV with evidence of active hepatitis.
6. Known history of positive HIV-1/HIV-2 antibodies (anti-HIV).
7. Anemia due to reasons other than iron deficiency (e.g., hemoglobinopathy and vitamin B12 or folic acid deficiency) that has not been corrected.
8. Administration and / or use of an investigational product (drug or device) within 30 days of screening.
9. Alcohol or drug abuse within the past six months.
10. Female participant who is pregnant or lactating, or sexually active females who are of childbearing potential not willing to use an acceptable form of contraceptive precautions during the study.
11. Unable to comply with study procedures and assessments.

4.3. Participant Assignment Process

Participants who satisfy the inclusion requirements and no exclusionary criteria will be eligible to participate in this study. This is an open label study.

4.4. Withdrawal from Study

Any participant who wishes to withdraw from the study may do so at any time without the need to justify their decision. The investigator may withdraw a participant from active study treatment at any time if it is felt to be in the best interest of the participant.

4.5. Discontinuation from Study Drug

Participants may elect to discontinue study drug, but wish to remain in the study for follow-up. In those situations, patients will be asked to continue the normal clinical trial schedule for ascertainment of safety events.

5. STUDY DRUG**5.1. Formulation, Packaging and Storage**

The investigational medication to be used in this study [supplied by American Regent, Inc.] will have been prepared according to Good Manufacturing Practices (GMP).

FCM (trade name, Injectafer[®]) will be supplied as 15 mL vials, containing 750 mg of iron as 5% w/v iron containing a polynuclear iron(III)-hydroxide 4(R)-(poly-(1→4)-O α -D-glucopyranosyl)-oxy-2 (R), 3(S), 5(R), 6-tetrahydroxy-hexonate complex in a solution of water for injection [50 mg/mL] and will be labeled according to FDA investigational regulatory requirements.

FCM must be kept in a secure place at the investigational site, and stored at room temperature (see United States Pharmacopeia). The study medication should not be frozen. Vials of FCM may not be used for more than 1 dose, or for more than 1 participant. All FCM vials and syringes (used and unused) should be kept by the study staff for reconciliation by the monitor. Following reconciliation, sites may destroy used and unused study drug on site using local procedures, provided a drug destruction policy is in place, or it may be returned to American Regent, Inc.

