6.3.2. Visit 2 Day 7 ± 1 day

All participants will return to the clinic on Day 7. Prior to the administration of the study drug, the participant will be evaluated clinically to assess for the development of clinically significant conditions that may contraindicate dosing.

- Vital signs (temperature, sitting heart rate and blood pressure)
- Blood samples for central lab hematology, chemistries and iron indices (prior to study drug administration).
- Concomitant medications assessment
- Verify amount of single FCM dose (15 mg/kg up to a maximum dose of 750 mg).
- Administer FCM as a slow IV injection at the rate of approximately 2 mL /minute or in no more than 250 mL of normal saline and infused over 15 minutes.
- Document start and stop time of FCM administration and the total dose administered and if diluted.
- Post-administration evaluation to include measurement of sitting heart rate and blood pressure immediately (within 5 minutes) after and 30 minutes after FCM administration.
- Adverse event / SAE assessment (starting at beginning of FCM injection).

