Timing: Non-serious AE will be reported from the initial treatment with FCM through the completion of the study Day 35. Adverse events will be captured 28 days post the last dose of study drug for participants who receive study drug and terminate early from the trial. This can be completed via a phone call. All ongoing AE's related to FCM should be followed until they are no longer related, have taken a confounding medication or return to baseline grade.

Relationship (Causality): The Investigator will be asked to document his/her opinion of the relationship of the event to the study drug* as follows:

- **NONE** There is *no* evidence of any causal relationship
- **UNLIKELY** There is *little* evidence to suggest there is a causal relationship. There is *another reasonable explanation* for the

event (e.g., the participant's clinical condition, other concomitant treatments).

- **POSSIBLE** There is *some* evidence to suggest a causal relationship (i.e. there is a reasonable possibility that the adverse experience may have been caused by the agent). However, the influence of *other factors may have contributed* to the event (e.g., the participant's clinical condition, other concomitant events).
- **PROBABLE** There is *evidence* to suggest a causal relationship, and the influence of other factors is *unlikely*

*For the purpose of this trial, study drug is defined as FCM.

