8.5.2. Adverse Events

Adverse events will be coded by system organ class (SOC) and preferred term (PT) using the Medical Dictionary for Regulatory Activities (MedDRA) dictionary.

The number and percent of participants who report treatment emergent AE (TEAE) will be summarized. A TEAE is an event with onset date on or after the study drug start date.

Adverse event summaries will exclude preferred terms that describe asymptomatic serum ferritin, TSAT, and reticulocyte values (or changes). This approach is justified by the reporting of these values in efficacy summaries and is consistent with the protocol-defined reporting standards for Hgb/hematocrit (Hct) and low iron indices. For the purposes of this study, non-serious anemia (Hgb or Hct below the normal range or worsened from baseline) or iron deficiency (iron indices below the normal range or worsened from baseline) will not be considered adverse events. Anemia or iron deficiency will be considered end points if an intervention is required.

The adverse event profile will be characterized with severity (as graded by the NCI-CTCAE) and relationship (unrelated and related) to study drug. Related adverse events will be events that are possibly or probably related to treatment in the investigator's judgment.

Participants who report the same preferred term on multiple occasions will be counted once for the preferred term: under the highest severity when summarized by severity and under the closest relationship to study drug when summarized by relationship. If a participant reports multiple preferred terms for a SOC, the subject will be counted only once for that SOC.

The number and percent of participants who report treatment-emergent serious adverse events will be similarly summarized for each treatment group. The number and percent of participants who report treatment-emergent adverse events resulting in discontinuation of study drug will be similarly summarized for each treatment group.

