3. STUDY SUBJECTS

3.1 DISPOSITION OF SUBJECTS

Disposition will be summarized for all screened subjects and the number of subjects in Safety Population will be summarized in each investigative site.

The disposition will include the following:

- Participants who are screened
- Participants who are included in Safety Population
- Participants who complete the study
- Participants who discontinue the study

The number and percent of subjects will be summarized for each reason for premature discontinuation.

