7.1 ADVERSE EVENTS

Adverse events (AEs) will be coded by System Organ Class (SOC) and Preferred Term (PT) using the Medical Dictionary for Regulatory Activities (MedDRA) dictionary. Adverse event

summaries will exclude preferred terms that describe asymptomatic serum ferritin, TSAT, and reticulocyte values (or changes). This approach is justified by the reporting of these values in efficacy summaries and is consistent with the protocol-defined reporting standards for hemoglobin/hematocrit and low iron indices. For the purposes of this study, non-serious anemia (hemoglobin or hematocrit below the normal range or worsened from baseline) or iron deficiency (iron indices below the normal range or worsened from baseline) will not be considered adverse events. Anemia or iron deficiency will be considered end points if an intervention is required.

A treatment-emergent adverse event (TEAE) is defined as an event with onset date on or after the study drug start date. Partial date TEAE classification rules refer to Section 2.3.4. Only TEAEs will be included in summary tables.

The incidence of TEAEs will be summarized as the number (percentage) of subjects with TEAEs within SOC and PT. Subjects who report the same PT on multiple occasions will be counted once for the PT: under the highest severity (severe > moderate > mild) CTCAE when summarized by severity and under the closest relationship (probably related > possibly related > unlikely related > none) to study drug when summarized by relationship. If a subject reports multiple PT for a SOC, the subject will be counted only once for that SOC. Events with unknown severity or relationship will be counted as unknown.

TEAEs will be summarized as below.

- An overview table, including number of subjects with
 - TEAEs
 - serious TEAEs
 - study drug related TEAEs
 - study drug related Serious TEAEs
 - TEAEs by severity
 - TEAEs leading to study drug discontinuation or withdrawal from study
 - TEAEs leading to death
- TEAE by SOC
- TEAE by PT
- TEAE by SOC and PT
- TEAE by SOC, PT, and Severity (CTCAE)
- Study drug related TEAEs by SOC, PT
- Serious TEAEs by SOC and PT
- Study drug related serious TEAEs by SOC and PT

- TEAEs leading to study drug discontinuation or withdrawal from study by SOC and PT
- TEAEs leading to death by SOP and PT

Unless otherwise stated, all TEAE tables will be sorted by SOC and PT in decreasing frequency of the number and percentage of subjects.

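### Follow-up after stopping study drug is stated only for children who elect to stop, and the SAP's adverse event tables combine stopping drug with leaving the study

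*Protocol*

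**What the plan says.** The course is two doses, on Days 0 and 7, so stopping study drug means not receiving the Day 7 dose.

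- Protocol 4.5 deals with the case where "Participants may elect to discontinue study drug, but wish to remain in the study for follow-up". Then "patients will be asked to continue the normal clinical trial schedule for ascertainment of safety events".
- Protocol 4.4, headed as withdrawal from the study, states that "The investigator may withdraw a participant from active study treatment at any time" when this serves the child's interest. It gives no instruction about later visits.
- Protocol 6.3.2 has each child examined before the second dose for "clinically significant conditions that may contraindicate dosing". It does not say which visits follow if that dose is withheld.
- Protocol 6.3.3 brings every participant back on Day 14. Section 6.3.5 asks for the Day 35 procedures before exit, whatever the reason for not completing.
- Protocol 7.1 says "Adverse events will be captured 28 days post the last dose of study drug for participants who receive study drug and terminate early", and allows this by telephone.
- Protocol 8.5.2 plans a summary of "treatment-emergent adverse events resulting in discontinuation of study drug". SAP 7.1 has instead, in both the overview and the detailed table, "TEAEs leading to study drug discontinuation or withdrawal from study". SAP 9 lists two changes from the protocol: LOCF and the laboratory grading scale.
- SAP 3.1 counts children who complete and "Participants who discontinue the study", with reasons, but has no line for stopping drug. SAP 5.1 and 5.2 summarize compliance and number of infusions.
- SAP 2.3.4 fills a missing Day 35 value by LOCF for the paired t-tests and leaves the descriptive summaries unimputed.

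**The concern.** The protocol foresees a one-dose child mainly through the investigator's check before the second dose. That is the case for which it states no follow-up. A site reading 4.4 by its heading could treat the child as out of the study, while a child who declines the second dose stays on schedule. Even for the child who elects to stop, the stated purpose is safety only, which leaves it unclear whether efficacy bloods are wanted.

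Two things are at stake. One is the late laboratory data in children stopped for a clinical reason: SAP 7.1.1 names hypophosphatemia first among the events of special interest, and SAP 7.2 plans a phosphate time course with days to return to normal, which needs later samples. The other is the primary endpoint, where a Day 35 Hgb that could have been drawn may be replaced by an early one.

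The SAP adds a reporting gap. Its combined category does not separate a child who could not take the second dose because of an adverse event from one who took both doses and left later.

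**Working it through.** **1. The rules side by side**

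| Situation | Where | Follow-up stated |
|---|---|---|
| Participant elects to stop drug | Protocol 4.5 | Normal schedule, for safety events |
| Investigator stops treatment | Protocol 4.4 | None |
| Day 7 dose withheld after examination | Protocol 6.3.2 | None |
| Any participant, Day 14 | Protocol 6.3.3 | Attends |
| Any early exit | Protocol 6.3.5 | Day 35 procedures before leaving |

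The last two rows favour continued visits or at least an exit assessment. Neither says whether a child stopped by the investigator is still in the study.

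**2. What is lost if a site treats the stop as an exit**

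Scheduled post-baseline samples fall on Days 7, 14, 28 and 35, which is 4. A child leaving at the Day 7 visit misses 3 of 4. The exit draw required by 6.3.5 then falls near Day 7, so it adds no later information. A child who attends Day 14 and then leaves misses 2 of 4.

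The documents do not say how an exit draw is labelled. SAP 2.3.3 summarizes by scheduled visit and defines no windows. If the draw is recorded as Visit 5, an early Hgb stands as a Day 35 value. If it is not, LOCF carries it forward. Either way the primary t-test uses an early value.

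**3. Adverse event window**

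Last dose day + 28: one dose gives 0 + 28 = Day 28; two doses give 7 + 28 = Day 35. Follow-up after the last dose is 28 days in both. A one-dose child who stays to Day 35 has 35 − 28 = 7 days more than a one-dose child who exits.

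**4. Effect on the mean Hgb change**

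The documents give no one-dose rate, dropout rate or Hgb trajectory, so there is no stated figure to reproduce. With N = 36 (the cap in SAP 1.3.3), k children carried from an early value, and d the rise each would have shown between that value and Day 35:

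reduction in mean change = (k / N) × d

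| k (assumed) | % of 36 | d = 0.5 | d = 1 | d = 2 g/dL |
|---|---|---|---|---|
| 1 | 2.8 | 0.014 | 0.028 | 0.056 |
| 2 | 5.6 | 0.028 | 0.056 | 0.111 |
| 4 | 11.1 | 0.056 | 0.111 | 0.222 |
| 6 | 16.7 | 0.083 | 0.167 | 0.333 |

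Both k and d are assumptions. The relevant d is the later rise after a single dose.

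**5. Can one-dose children be seen in the planned output?**

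If k of N children had one infusion and the rest two, mean = 2 − k/N and SD = √[k(N − k) / (N(N − 1))]. At N = 36:

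- k = 1: mean 2.0, SD √(35/1260) = 0.17
- k = 2: mean 1.9, SD √(68/1260) = 0.23
- k = 4: mean 1.9, SD √(128/1260) = 0.32
- k = 6: mean 1.8, SD √(180/1260) = 0.38

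At the precision set in SAP 2.1.1, mean and SD together identify k for every value from 0 to 12. The number is recoverable; the reason, and who decided, are not.

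**The case against.** The strongest reply is that nothing tells a site to send the child home. Section 4.4 speaks of withdrawal from treatment, Day 14 is for everyone, Visits 4 and 5 carry no on-drug condition, and 6.3.5 secures a full exit assessment including hematology, chemistry with phosphorus, and iron indices. That is right. A reader might infer that a child stopped by the investigator leaves with only a telephone call; the documents do not support that. What survives is that an exit assessment done near Day 7 cannot supply Day 14, 28 or 35 values.

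A reader might also infer that these children get shorter adverse event follow-up. Measured from the last dose it is 28 days in either case. Related adverse events still ongoing, serious events, and end-of-study laboratory values judged clinically significant are also followed further (Protocol 7.1 and 7.3). This softens the phosphate argument but does not remove it, because a fall arising after exit would not be sampled.

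A third tempting reading is that one-dose children go uncounted. SAP 5.1 and 5.2 show otherwise. Counting a one-dose child who attends Day 35 as a completer follows the protocol's own definition of completion in 6.3.5. The two states are combined only in the adverse event tables; the disposition table simply omits drug discontinuation.

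Finally, SAP 9 claims to list only major changes, so the silence there is a minor matter. The substitution itself remains a departure from Protocol 8.5.2.

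**Conclusion.** The point holds in limited form. The protocol's one explicit off-drug rule covers elective stops and gives a safety purpose only; the investigator's stop and the withheld Day 7 dose have no rule, and the heading of 4.4 does not match its wording on treatment. Loss of later samples is possible under one reading, not directed.

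Its size is unknown. Each child who exits near Day 7 loses 3 of 4 post-baseline samples; the reduction of 0.01 to 0.33 g/dL in the mean change rests wholly on assumed values of k and d. If Hgb rises after the early value, LOCF understates the benefit, so this is not evidence of an inflated result.

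The SAP point needs no assumption: the protocol promises adverse events leading to drug discontinuation, and the SAP gives them only combined with study withdrawal.

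**What to change.** 1. Reconcile Protocol 4.4, 4.5, 6.3.2, 6.3.3 and 6.3.5. Keep stopping study drug, by participant or by investigator, distinct from withdrawal from the study, and in both cases request the assessments already scheduled to Day 35, including Hgb, iron indices and chemistry. This concerns data collection only and leaves untouched when or why treatment is stopped.
2. In SAP 7.1, report treatment-emergent adverse events leading to drug discontinuation separately from those leading to study withdrawal, in both the overview and the detailed table. This restores what Protocol 8.5.2 specifies.
3. Optional: a disposition row for doses received, with the reason for a missed dose. This is a reporting preference, since infusions and compliance are already summarized.

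The cost is a few sentences of protocol text, one extra table, and a few more attended visits for children who might otherwise have left.
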